## **7 Safety and Adverse Events**

This is an observational study so safety reporting will not be applicable

### **7.1 *Definitions***

### **7.2 *Recording of Adverse Events***

### **7.3 *Reporting of Serious Adverse Events***

#### **7.3.1 Study Sponsor Notification by Investigator**

#### **7.3.2 Notification to Research Institute by Investigator**

### **7.4 *Unblinding Procedures***

### **7.5 *Stopping Rules***

### **7.6 *Medical Monitoring***

#### **7.6.1 Internal Data and Safety Monitoring Board**

#### **7.6.2 Independent Data and Safety Monitoring Board**

## **8 Data Handling and Record Keeping**

### ***8.1 Confidentiality***

Information about study subjects will be kept confidential. In the event that a subject revokes authorization to collect or use protected health information (PHI), the investigator, by regulation, retains the ability to use all information collected prior to the revocation of subject authorization. For subjects that have revoked authorization to collect or use PHI, attempts should be made to obtain permission to collect at least vital status (i.e. that the subject is alive) at the end of their scheduled study period.

### ***8.2 Handling and storage of data and documents***

All personal data will be coded by serial numbers. Only the investigators will have the access to the key. Statistics will be performed with the coded numbers. Published data from this study cannot be traced to a specific infant.

All data requested on the case report form (CRF) must be recorded. All missing data must be explained. If a space on the CRF is left blank because the procedure was not done, write “N/D”. If the item is not applicable to the individual case, write “N/A”. If any entry error has been made, to correct such an error, draw a single straight line through the incorrect entry and enter the correct data above it. All such changes must be initialed and dated.

### ***8.3 Records Retention***

All coded data will be stored in a security place for a minimum of ten years.

## **9 Ethical Considerations**

This study is to be conducted according to applicable government guidelines and regulations and Institutional research policies and procedures.

This protocol and any amendments will be submitted to the Ethical Committee at Bao'an Maternal and Child Hospital, Shenzhen for formal approval of the study conduct. The decision of the Ethical Committee concerning the conduct of the study will be made in writing to the investigators.

All subjects for this study will be provided a consent form in Chinese describing this study and providing sufficient information for subjects to make an informed decision about their participation in this study. The consent form will be submitted with the protocol for review and approval by the Ethical Committee for the study. The formal consent of a subject must be obtained before that subject is submitted to any study procedure. This consent form must be signed by the subject or legally acceptable surrogate, and the investigator-designated research professional obtaining the consent.

Blood samples obtained for this cohort are left-over sample materials from routine clinical blood sampling for screening and diagnosis in preterm infants at the local hospital (Neonatal Department, Bao'an Maternal and Child Health Hospital, Shenzhen). Therefore, there are no potential harmful effects of blood sampling to the participating infants.

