### 3 Study Design

#### 3.1 General Design

- This observational prospective cohort study includes 200 preterm infants, born < 32 weeks of gestation, at Neonatal Department, Bao'an Maternal and Child Health Hospital, Shenzhen, Guangdong, China.
- Patients, who fulfill inclusion criteria, will be recruited following the parental consent. The recruitment stops when the sample size reaches 200. Expected study duration: January 2017-June 2018.
- Patients will follow usual clinical procedures at the hospital. Patient groups will be categorized based on clinical records: infants born without and with clinical chorioamnionitis, infants without or with at least one episode of late-onset sepsis (LOS) and/or necrotizing enterocolitis (NEC).
- Enrollment and sampling are performed as indicated in the diagram below. Blood sampling is performed every week from birth until 4 weeks of age, or until discharge

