### 4.3 Subject Recruitment and Screening

When infants are admitted to the Neonatal department, parents are informed about this observational study and the possibility to participate by the principal investigator. Signed parenteral consent is required to enter the study. Subjects should be recruited and the first blood sampling will be performed within the first 48 h of life.

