### 4.4 Withdrawal of Subjects

A subject will be withdrawn from the study in one of the following conditions:

- The consent is withdrawn by parents prior to the expected completion of the patient
- The principal investigator reserves the right during the study to withdraw a patient from the study if the patient's conditions are evaluated to be not suitable for blood sampling. In this occasion, another patient needs to be recruited to replace the drop-out patient.
- Any infants that die before the completion of 4 postnatal weeks and are not diagnosed with LOS, NEC or chorioamnionitis beforehand will be withdrawn from the study. In this occasion, another patient needs to be recruited to replace the drop-out patient.

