## 5 Study Procedures

Care of patients follows standard procedures established by the local hospital. Blood samples will be taken according to the study design. At each blood sampling period, the study investigator will evaluate the suitable blood volume to be taken, based on body weight, health status and other guidelines from the hospitals.

Feeding regime follows the practice at the local NICU: mother's own milk is the first priority, followed by donor milk and infant formula. For each time of feeding, the following details are noted in the feeding CRF: time, type of feeding (mother's milk, donor milk, formula), feeding volume, gastric residual from previous feeding. For feeding intolerance, any interventions such as aspiration, decreased the amount of feeding or stop feeding are noted in the comments section of the CRF.

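### Section 9 calls the samples left-overs of routine care and concludes that sampling cannot harm, but sections 4.4 and 5 contain rules that make sense only if the study influences the draw

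*Protocol*

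**What the plan says.** Section 9 (Ethical Considerations) describes the source of the blood: "Blood samples obtained for this cohort are left-over sample materials from routine clinical blood sampling for screening and diagnosis in preterm infants". The next sentence draws the safety conclusion: "Therefore, there are no potential harmful effects of blood sampling to the participating infants". No other reason is given for it.

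Four other sections describe sampling:

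- **Section 3.1** sets the calendar: "Blood sampling is performed every week from birth until 4 weeks of age, or until discharge".
- **Section 4.3** says that "the first blood sampling will be performed within the first 48 h of life", and links this to recruitment.
- **Section 5** says that care follows the hospital's standard practice, then says separately that blood is drawn as the study design requires. At each sampling period "the study investigator will evaluate the suitable blood volume to be taken", with reference to the infant's weight, state of health and hospital guidance.
- **Section 4.4** lets the principal investigator withdraw an infant whose condition is judged "not suitable for blood sampling", and requires a replacement.

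Section 6.2 analyses the -omic data as a weekly series.

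**The concern.** The document gives two accounts of where the blood comes from. In one, the study keeps what remains after the hospital has drawn blood for its own purposes. In the other, the study has a say in whether blood is drawn and how much. The no-harm sentence follows only from the first.

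Two things are at stake.

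1. **The statement to the ethics committee.** Section 9 says the protocol is submitted for formal approval. The participants are infants born before 32 weeks, and sections 4.4 and 5 themselves treat sampling as something that depends on the infant's condition.
2. **The meaning of a missing or extra sample.** A draw made on a fixed routine and a draw prompted by clinical suspicion do not carry the same information. If some samples are by-products of diagnostic draws, their timing and availability may be related to illness. Illness defines one of the primary comparisons, infants with versus without late-onset sepsis and/or NEC.

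**Working it through.** The protocol gives no figure to reproduce here. The check is to take each sampling rule and ask whether it can stand if only left-over blood is used.

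| Rule | Section | Compatible with left-overs only? |
|---|---|---|
| Weekly sampling to 4 weeks or discharge | 3.1 | Yes, if the unit draws routinely about once a week and residue is kept |
| First sample within 48 hours of life | 4.3 | Yes, if a routine draw falls in that window |
| Blood drawn as the study design requires, stated apart from standard care | 5 | Hard to reconcile |
| Study investigator judges the volume to draw from weight and state of health | 5 | No: these are criteria for drawing from an infant, not for keeping residue from a tube already filled |
| Withdrawal and replacement when the infant is unfit for sampling | 4.4 | No evident purpose: keeping residue places no burden on the infant |

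The schedule and the 48-hour window are therefore not contradictory in themselves. The conflict lies between section 9 and the volume and withdrawal rules in sections 5 and 4.4.

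The no-harm sentence is introduced as a consequence of the left-over source. If any part of the timing or volume is study-driven, that premise fails for those draws and the protocol offers no other support for "there are no potential harmful effects of blood sampling to the participating infants".

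**Scope.** Assuming one sample at birth and one at each of weeks 1 to 4, the ceiling is 5 × 200 = 1,000 samples. The number analysed will be lower. Collection ends at discharge (section 3.1), and section 5.3 limits the analysis to samples up to diagnosis or completion of four weeks.

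Section 6.1 expects clinical late-onset sepsis and/or NEC in 20–30% of infants, which is 0.20 × 200 = 40 to 0.30 × 200 = 60. This is the group whose sample timing could depend on illness.

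**What can be recovered from the CRF.** Section 5.2 lists the time and volume of each sample and the day of life at diagnosis, so timing relative to diagnosis is available. It does not list why the blood was drawn. From the listed items, a routine weekly draw cannot be told apart from one prompted by symptoms.

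**The case against.** The best defence is that the weekly draws are the unit's own and the study keeps the residue. Section 3.1 says infants receive the hospital's ordinary care, section 5.3 describes collection after diagnosis as routine, and section 9 mentions screening as well as diagnosis. Screening draws need not be triggered by illness. This stands as an explanation of the schedule, but it does not explain the volume and withdrawal rules. A variant is that the investigator only decides how much to add to a routine draw. On that reading the added volume is study-driven, and the no-harm conclusion again does not follow.

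On wording, section 9 does not say that every sample is a left-over, and section 5 has the investigator evaluate the volume partly under hospital guidelines, not fix it freely. Both points are fair. The statement in section 9 is nevertheless unqualified, and no exception is named.

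The sampling diagram in section 3.1 and the CRF in the appendix are not visible in the text at hand. Either might show how study samples relate to routine draws or record the type of draw. That limits the CRF point, but it does not remove the conflict between the written sections.

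A reader might infer three stronger things that the document does not support:

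- **That section 7 loses its basis.** Section 7 says "safety reporting will not be applicable" because the study is observational, and section 3.4 gives the same reason. Neither relies on left-over blood.
- **That sicker infants contribute more samples.** Under section 5.3, samples count only up to diagnosis or four weeks, which could equally leave affected infants with fewer.
- **That purely scheduled draws would be free of the problem.** Discharge and withdrawal of unfit infants also make availability depend on the infant's condition.

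**Conclusion.** The protocol contradicts itself on the source of the blood samples. The left-over account in section 9 cannot readily be squared with the volume rule in section 5 or the withdrawal rule in section 4.4. The no-harm statement is therefore unsupported as written. This does not show that sampling is harmful, nor which sampling rule is the right one; it shows that the stated reason for excluding harm does not match the protocol's own procedures.

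The conflict concerns the described source of every sample, at most 1,000 under the five-sample assumption. The protocol gives no split between routine, clinically indicated and study-driven draws, so neither the number of samples outside the left-over description nor the direction or size of any effect on the comparison can be determined. Illness-dependent timing is a possibility to be examined, not a demonstrated bias.

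The correction should be made: it is inexpensive, and it bears both on what the ethics committee was told and on how the weekly series is read.

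**What to change.** 1. Reconcile sections 3.1, 4.3, 4.4, 5 and 9 so that they give one account of where the samples come from. Which sampling rule applies is for the investigators and the ethics committee to settle.
2. If any timing or volume is study-driven, correct the no-harm statement in section 9 that goes to the ethics committee.
3. Add one CRF item to the list in section 5.2 recording whether each sample came from a scheduled routine draw, a clinically indicated draw or a study-driven draw. With the sampling time and day of diagnosis already listed, this lets illness-dependent timing or availability be examined in the comparison of infants with and without late-onset sepsis and/or NEC.

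The cost is protocol wording, one CRF field and possibly a notification to the ethics committee. It needs no change to the sample size or to the three planned comparisons.

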## **10 Study Finances**

### ***10.1 Funding Source***

The analytical part of the study will be partly funded by NEOCOL research grant by Innovation Fund Denmark ([name] as the grant holder). Additional funding will be searched locally in Shenzhen by MD [name].

### ***10.2 Conflict of Interest***

All investigators declare no potential conflicts of interest

### ***10.3 Subject Stipends or Payments***

Not applicable

## **11 Publication Plan**

The data are considered joint ownership between the study collaborators and Bao'an Maternal and Child Health Hospital, Shenzhen. All results derived from this study will be published jointly between these two institutions in pediatrics, nutrition or immunology journals.

Neither the complete nor any part of the results of the study carried out under this protocol will be published or passed on to any third party without the consent of all the study investigators. Any investigator involved with this study is obliged to provide the principal investigator with complete test results and all data derived from the study.

## **13 Appendices**

- Parental Consent Form (in Chinese)
- CRF (both English and Chinese)
